be converted to 100 and a score of 0 will remain as 0. This QOL will be measured weekly for the entire 12 week length of the study and at the end of the intervention. QOL improvement will be defined as at least a 10 point increase in the QOL score from baseline, on the percentage scale. This 10 point change represents a clinically meaningful improvement in QOL based on work done by Jeff Sloan [17]. The date at which the QOL score is first known to increase by at least 10 from baseline (on the 100 point scale), will be considered the event date for the purpose of analysis. Patients without at least a 10 point increase in QOL from baseline, will be censored on their last QOL evaluation date up to a maximum of 12 weeks. We will enter a total of 70 evaluable patients (35 per arm) using a 1:1 randomization scheme. The primary analysis will be a comparison of oral SBI vs. placebo using a two-sided log-rank test between the 2 Kaplan-Meier curves [18]. This analysis will take place after an approximate 16 month accrual period, and after 66 total events across both arms combined (which should happen after about 12 weeks of follow-up in all evaluable patients). Additionally, we assume a constant accrual rate over the course of the study, and that no patients will drop-out of the study, since historically the lost to follow-up rate is <1%. To determine the appropriate sample size of 35 evaluable patients per arm, we assumed exponential survival and that the median time-to-QOL improvement is around 3 weeks in the oral SBI arm and 6 weeks in the placebo arm (HR=2). This hazard ratio is based on our institution's data which shows that patients often begin postoperative chemotherapy 6 weeks after surgery. These assumptions yield 80% power to detect a significant difference between the arms using a 2-sided log-rank test at alpha=0.05. All patients who meet the eligibility criteria, sign the consent form, and are randomized, will be considered evaluable for this endpoint. All eligible patients will be followed a maximum of 12 weeks. If the 2-sided log-rank test p-value is < 0.05 showing significantly shortened time-to-QOL improvement in the oral SBI arm as compared to placebo, further study will be warranted. Of course, any final decisions will be based on all primary and secondary endpoints.

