- 16.2 Sample Size: The study design to be utilized is fully described in Section 16.11 (see above). There will be 35 evaluable patients randomized to each arm of this study. We anticipate accruing an additional 15 patients to each arm to account for ineligibility, cancellation, major intervention violation, or other reasons. Therefore, maximum accrual is 100 patients (50 per arm).
- 16.3 Accrual Time and Study Duration: The anticipated accrual rate is approximately 4-5 patients per month. Therefore, the accrual period for this randomized Pilot study is expected to be around 24 months. The final analysis can begin approximately 28 months after the trial begins, i.e., as soon as the last patient registered has been observed for 4 months.
- 16.4 Other Considerations: Adverse events as well as scientific discoveries or changes in standard care will be taken into account in any decision to terminate the study.

16.5 Data & Safety Monitoring:

16.51 The principal investigator(s) and the study statistician will review the study at least twice a year to identify accrual, adverse event, and any endpoint problems that might be developing. The trial is monitored continually by the study team who are notified of every grade 4 and 5 event in real time. The Mayo Clinic Cancer Center (MCCC) Data Safety Monitoring Board (DSMB) is responsible for reviewing accrual and safety data for this trial at least twice a year, based on reports provided by the MCCC Statistical Office.

16.52 Adverse Event Stopping Rules: The stopping rules specified below are based on the knowledge available at study development. We note that the Adverse Event Stopping Rule may be adjusted in the event of either (1) the study re-opening to accrual or (2) at any time during the conduct of the trial and in consideration of newly acquired information regarding the adverse event profile of the intervention(s) under investigation. The study team may choose to suspend accrual because of unexpected adverse event profiles that have not crossed the specified rule below. CTCAE v4.0 will be used to determine grading for these stopping rules.

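### Section 16.11: 70 patients capped at 12 weeks give about 59 events and about 76% power, not 66 events and 80%

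*Combined protocol and SAP*

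**What the plan says.** Section 16.11 bases the sample size on 35 evaluable patients per arm, 1:1 allocation, exponential event times, constant accrual and no dropout. It assumes that "the median time-to-QOL improvement is around 3 weeks in the oral SBI arm and 6 weeks in the placebo arm", which it states as HR=2, and concludes: "These assumptions yield 80% power to detect a significant difference between the arms using a 2-sided log-rank test at alpha=0.05".

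Follow-up is limited in two places in that section. Patients without an event are censored at their last QOL assessment, at 12 weeks at the latest, and "All eligible patients will be followed a maximum of 12 weeks".

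On timing, 16.11 expects roughly 16 months of accrual and sets an event condition on the primary analysis, which is to be done "after 66 total events across both arms combined (which should happen after about 12 weeks of follow-up in all evaluable patients"). On the analysis set it says: "All patients who meet the eligibility criteria, sign the consent form, and are randomized, will be considered evaluable for this endpoint".

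Section 16.2 repeats 35 evaluable patients per arm and adds: "We anticipate accruing an additional 15 patients to each arm to account for ineligibility, cancellation, major intervention violation, or other reasons". The ceiling it sets is 100 patients in total, 50 in each arm. Section 16.3 expects 4 to 5 patients per month and about 24 months of accrual. It starts the final analysis at about month 28, once the last registered patient has been observed for 4 months, and mentions no event count.

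**The concern.** The number of events needed for a given power and the number a design will yield are separate quantities. Section 16.11 gives 66 for both. Under a 12-week cap and a 6-week placebo median, a quarter of placebo patients are expected to be censored without an event, so 66 events from 70 patients looks too many.

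Two things depend on this. The first is the stated power of the test whose p-value, under 16.11, decides whether further study is warranted. The second is the timing of the primary analysis: if 66 events cannot realistically occur in 70 patients, 16.11 sets a condition that will not be met, while 16.3 gives a calendar rule that ignores it. A statistician holding fewer than 66 events could not tell which section governs.

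**Working it through.** **Inputs, all from 16.11:** n = 35 per arm; medians 3 weeks (SBI) and 6 weeks (placebo); HR = 2; exponential times; no dropout; maximum follow-up 12 weeks; two-sided log-rank test at 0.05.

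**1. Reproduce the plan's 66.** Schoenfeld's formula for events required at 80% power:

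d = 4 × (1.96 + 0.8416)² / (ln 2)² = 65.35, rounded up to 66.

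Power at 66 events is 80.4%. So 66 is right as a requirement.

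**2. Events expected under the cap.** P(event by week 12) = 1 − 2^(−12/median):

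- SBI: 1 − 2^(−4) = 0.9375, so 35 × 0.9375 = 32.81 events
- Placebo: 1 − 2^(−2) = 0.75, so 35 × 0.75 = 26.25 events
- Total: 59.06 events

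SD = √[35 × (0.9375 × 0.0625 + 0.75 × 0.25)] = 2.93, with a 95% range of 53 to 64. Convolving the two binomial distributions gives P(at least 66 events) = 0.0086.

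**3. Power at the expected count.** Power = Φ(√E / 2 × ln 2 − 1.96) = Φ(√59.06 / 2 × 0.6931 − 1.96) = 75.9%. Other methods at 35 per arm:

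- Log-rank simulation, 20,000 runs (Monte Carlo SE about 0.3 points): 76.0% with exact event times, 75.6% with weekly assessment
- A separate 6,000-run simulation: 77.0% and 76.0%
- Variance 1/d1 + 1/d2: 75.4%
- Lachin-type exponential test: 73.3%
- Freedman: 72.6%

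All fall below 80%. The hazard ratio detectable with 80% power is exp(2 × 2.8016 / √59.06) = 2.07.

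**4. How many patients would give 66 events.** The mean event probability is (0.9375 + 0.75) / 2 = 0.84375, and 66 / 0.84375 = 78.2 patients.

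| Per arm | Total | Expected events | P(at least 66) | Power (Schoenfeld) |
|---|---|---|---|---|
| 35 | 70 | 59.1 | 0.9% | 75.9% |
| 39 | 78 | 65.8 | 55% | 80.3% |
| 40 | 80 | 67.5 | 74% | 81.3% |
| 42 | 84 | 70.9 | 95% | 83.1% |
| 50 | 100 | 84.4 | over 99.9% | 88.9% |

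Simulated power at 39, 40 and 50 per arm (exact times) was 79.9%, 80.9% and 88.9%.

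**5. A possible source of the discrepancy.** Drop the cap, so that patients enter uniformly over 16 months and all are followed until 12 weeks after the last entry. Then 70 patients give 68.8 expected events and about 82% power by Schoenfeld (79% simulated). The stated figures fit a calculation without the cap. That it was done this way is an inference; that the cap and the figures conflict is arithmetic. With equal follow-up for everyone, 66 events from 70 patients would take about 19.6 weeks each.

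**6. Accrual periods.** At 4 to 5 per month, 70 patients take 14 to 17.5 months and 100 take 20 to 25 months. The 16 months in 16.11 and 24 months in 16.3 therefore fit 70 and 100 patients, though the text does not say so.

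**The case against.** The strongest reply is that more than 70 patients may be analysed. Section 16.11 counts every eligible, consented, randomized patient as evaluable, so of the losses named in 16.2 only ineligibility clearly removes anyone, and accrual may reach 100. With 84 analysed, 66 events occur with 95% probability and power is 83%. This stands as a description of what could happen, and it limits the practical harm. It does not support the text: 16.11 derives its power from 35 per arm, and 16.2 keeps 35 per arm as the evaluable number, with the rest as cover for losses.

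A second reply is that the medians are only approximate. Moving the SBI median alone to 2.9 weeks (HR 2.07) brings power at 35 per arm to 79.9%. But the section fixes HR=2, an SBI median of 3.2 weeks gives 67%, and the event count stays near 59 either way. With HR held at 2, medians of 2.5 and 5 weeks give 62.1 events and 78.0% power, while 3.5 and 7 weeks give 56.1 and 73.7%. Reaching 66 expected events by week 12 would need medians of about 1.8 and 3.7 weeks.

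Third, this is a pilot, a gap of about 4 points is modest, and 16.3 already offers a workable time-based start for the analysis. All of that is true. It argues for a small correction, not for leaving the figures as they are.

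**Conclusion.** The concern holds. For 70 patients capped at 12 weeks, the plan's inputs give about 59 events and about 76% power (73% to 77% across methods), against the stated 66 and 80%. At that size the event condition has under a 1% chance of being met, and further waiting cannot change this. The result rests on 16.11's own assumptions: exponential times, medians of 3 and 6 weeks, and no dropout; any dropout would lower the event count further. The test, the alpha level and patient safety are unaffected. The figures and the analysis trigger should be corrected; the design need not change.

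**What to change.** Correct 16.11 in one of two ways, at the sponsor's choice.

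- **A (the simpler edit).** Keep 70 evaluable patients and state about 59 expected events and about 76% power for HR=2 with follow-up capped at 12 weeks. Because accrual may run past 70, it helps to add the power at larger evaluable numbers (78: 80%; 100: 89%) and to say whether accrual stops at 70 evaluable patients. Cost: stated power falls by about 4 points.
- **B.** Keep 80% power and HR=2 by raising the evaluable target to 78 to 80 (39 to 40 per arm), and amend 16.2 to match. Cost: within the ceiling of 100, the allowance for losses falls from 30 patients to 20 to 22.

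Under either option, replace the 66-event condition with one rule worded identically in 16.11 and 16.3, for example: *The primary analysis will be done once the last patient registered has been observed for 4 months, so that all week-12 PQL data are in, whatever the number of events.*

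A sentence in 16.11 linking 16 months to 70 patients and 24 months to the maximum of 100 would also help, but is optional. The edits are wording only; the test, alpha, visits and accrual ceiling stay as they are.

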10.6 Required Routine Reporting

Adverse events to be graded at each evaluation and preintervention symptoms/conditions to be evaluated at baseline per the CTCAE v4.0 grading unless otherwise stated in the table below:

System Organ Class (SOC)	Adverse event/Symptoms	Baseline	Each evaluation
Gastrointestinal disorders	Abdominal pain	X	X
	Bloating	X	X
	Diarrhea		X
	Baseline number of stools per day	X	
	Flatulence	X	X
	Nausea	X	X
	Vomiting	X	X
General disorders and administration site conditions	Fatigue	X	X
Infections and infestations	Wound infection	X	X
Injury, poisoning and procedural complication	Wound complication	X	X
	Wound dehiscence	X	X

10.61 Submit via appropriate MCCC Case Report Forms (i.e., paper or electronic, as applicable) the following AEs experienced by a patient and not specified in Section 10.6

10.611 Grade 2 AEs deemed *possibly, probably, or definitely* related to the study intervention or procedure.

10.612 Grade 3 and 4 AEs regardless of attribution to the study intervention or procedure.

10.613 Grade 5 AEs (Deaths)

10.6131 Any death within 30 days of the patient's last study treatment or procedure regardless of attribution to the study intervention or procedure.

10.6132 Any death more than 30 days after the patient's last study intervention or procedure that is felt to be at least possibly intervention related must also be submitted as a Grade 5 AE, with a CTCAE type and attribution assigned.

11.0 Intervention Evaluation: None**12.0 Descriptive Factors: None****13.0 Follow-up Decision at Evaluation of Participants**

- 13.1 Participants will receive 3 cycles of therapy (12 weeks) with oral SBI or placebo, followed by a 4 week observation visit. No additional follow-up is required for these patients beyond the 4 week observation time point.
- 13.2 Participants who go off the intervention early for unacceptable adverse events or patient refusal of further treatment will go to the observation phase. Patients can continue in the observation phase for total of 16 weeks of study participation.
- 13.3 Participants where post-operative problems occur, study treatment cannot begin, and participant agrees to complete questionnaires will crossover to QOL assessment only. These participants will be followed per the test schedule (Section 4.0).

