- 13.4 A participant is deemed *ineligible* if after registration, it is determined that at the time of registration, the participant did not satisfy each and every eligibility criteria for study entry. The patient will go directly off study.
 - If the participant received therapy, all data up until the point of confirmation of ineligibility must be submitted.
 - If the participant never received therapy, on-study material must be submitted.
- 13.5 A participant is deemed a *major violation*, if protocol requirements regarding intervention in cycle 1 of the initial intervention are severely violated that evaluability for primary end point is questionable. All data up until the point of confirmation of a major violation must be submitted. The patient may continue therapy off-protocol at the discretion of the physician as long as there are no safety concerns, and the patient was properly registered.
- 13.6 A participant is deemed a *cancel/withdrawal* if he/she is removed from the study for any reason before any study intervention is given or participant does not agree to crossover to QOL assessment only. On-study material and the End of Active Intervention/Cancel Notification Form must be submitted. No further data submission is necessary.

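### The 80% power assumes no drop-out, but the plan counts cancellations and never-starters as evaluable and does not settle whether accrual stops at 70 or 100

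*Combined protocol and SAP*

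**What the plan says.** All references are to the combined protocol and SAP.

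- **Sizing (16.11).** 35 evaluable patients per arm, exponential times, medians of 3 and 6 weeks, hazard ratio 2. "These assumptions yield 80% power to detect a significant difference between the arms using a 2-sided log-rank test at alpha=0.05". The same section says "we assume a constant accrual rate over the course of the study, and that no patients will drop-out of the study", citing a historical lost-to-follow-up rate below 1%.
- **Who is evaluable (16.11).** "All patients who meet the eligibility criteria, sign the consent form, and are randomized, will be considered evaluable for this endpoint". Starting product is not a condition.
- **Reserve (16.2).** "We anticipate accruing an additional 15 patients to each arm to account for ineligibility, cancellation, major intervention violation, or other reasons". This takes the maximum to 50 per arm, 100 in all.
- **Never-starters (13.3).** "Participants where post-operative problems occur, study treatment cannot begin, and participant agrees to complete questionnaires will crossover to QOL assessment only".
- **Cancellations (13.6).** For patients removed before any product is given, or who decline the questionnaire-only option: "On-study material and the End of Active Intervention/Cancel Notification Form must be submitted. No further data submission is necessary".
- **Timing.** 16.11 places the analysis after about 16 months of accrual and 66 events, with follow-up capped at 12 weeks per patient. 16.3 gives 4-5 patients per month and about 24 months of accrual.

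**The concern.** The reserve and the evaluability rule do not fit together. Under 16.11 an eligible patient who cancels, or who never starts, already occupies one of the 70 places. Under 16.2 a cancellation is a loss for which an extra patient is recruited. Ineligible patients are replaced on either reading. Eligible cancellations and never-starters are replaced only if 16.2 prevails.

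Such losses are foreseeable. Patients register within 7 days of major surgery (3.14), product may start up to 7 days after registration (6.16), and 13.3 and 13.6 exist to handle those who do not start. The lost-to-follow-up figure covers neither group.

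A cancelled patient gives no post-baseline score and so no event. A followed never-starter in the SBI arm dilutes the hazard ratio. Neither effect is in the 80%. Section 16.11 makes p < 0.05 the signal for further study, so a null result could be read as a negative at 80% power when the analysis had less.

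**Working it through.** **1. The plan's own figure.** Schoenfeld's formula, two-sided 0.05, 80% power, 1:1, hazard ratio 2: d = 4(1.960 + 0.842)² / (ln 2)² = 65.3, rounded up to 66. Power at 66 events is Φ(√66 × ln 2 / 2 − 1.960) = 80.4%. The stated figures reproduce.

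**2. Events from 70 patients with no losses.** With the 12-week cap, the probability of an event is 1 − 2^(−12/3) = 0.9375 on SBI and 1 − 2^(−12/6) = 0.75 on placebo. Expected events are 35 × (0.9375 + 0.75) = 59.1, and power is Φ(√59.1 × 0.3466 − 1.960) = 75.9%. Reaching 66 events needs 66 / 1.6875 = 39.1, so 40 per arm. Without the per-patient cap, 16 months of uniform accrual plus 12 weeks gives 68.8 events, so 70 patients fit 66 events only if the cap is ignored. This shortfall belongs to the cap, not to drop-out, and is kept separate below.

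**3. The accrual stop.** At 4-5 patients per month, 16 months gives 64 to 80 patients and 24 months gives 96 to 120. The first matches a stop near 70, the second a stop near 100.

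**4. Power with losses.** The documents give no rate, so 10 to 30% per arm is an assumption. Its upper end is the whole reserve, 15/50. Inputs otherwise follow the plan: hazards ln 2/3 and ln 2/6 per week, 12-week cap, two-sided 0.05. Cancelled patients are censored at time 0. Never-starters are followed at the placebo hazard in both arms, which is also an assumption. Simulated log-rank power (2,000 runs per cell at 35 per arm, 1,500 at 50; standard error about 1 point):

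| Randomised per arm | Type of loss | 10% | 20% | 30% |
|---|---|---|---|---|
| 35 | all cancelled | 71% | 66% | 58% |
| 35 | even mix | 68% | 57% | 50% |
| 35 | all never-starters, followed | 66% | 53% | 44% |
| 50 | all cancelled | 85% | 81% | 76% |
| 50 | all never-starters, followed | 80% | 69% | 56% |

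The no-loss references are 76% at 35 per arm and 89% at 50 per arm.

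Fixed counts with 8,000 runs agree to within a few points. At 35 per arm, 3 cancelled gives 72%, 10 never-starters 43%, and 5 of each 50%. At 50 per arm, 15 cancelled gives 75%, 15 never-starters 55%, and 7 cancelled plus 8 never-starters 63%. Allowing for simulation error and for fixed or random counts, the ranges are about 42 to 73% at 70 patients and about 55 to 85% at 100.

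**The case against.** The strongest reply is that the plan does provide for replacement. Section 16.2 names cancellation, and 16.3 plans accrual for about 100. The 66-event condition points the same way: 70 patients are not expected to meet it, cancelled patients add no events, and a trial held to 66 events would have to keep recruiting. For example, 44 per arm with 5 cancelled gives about 66 events and 79% power. This stands as far as it goes. A reader might infer that the reserve never replaces cancellations and never-starters and that power therefore falls to 50-70%. The documents do not support that: it needs the 16.11 definition to override 16.2, a stop at 70, and a loss rate that is nowhere given. But the text does not tie accrual to events either, and the 16-month figure favours a stop near 70.

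Four further points stand in part:

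- The 30% is a reserve ceiling, not a forecast of cancellation. It also covers ineligibility, and major violations (13.5) in patients who may have been treated.
- The largest losses of power come from never-starters entering the log-rank test at the placebo hazard. Section 16.63 describes their data only as exploratory, and 13.3 patients have postoperative problems, so that hazard is uncertain. The 16.11 rule nevertheless includes them.
- A reader might also infer that, even at 100 patients, 80% power fails once more than 10% go untreated. That is so for followed never-starters only; with 20% cancelled, power is still about 81%.
- The trial is a pilot, and 16.11 bases final decisions on all endpoints. That lowers the stakes but does not make the printed power right.

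**Conclusion.** The point holds as an inconsistency with consequences for power. Section 16.11 prints 80% on the basis of no drop-out and the full effect in all 70 evaluable patients, yet its evaluability rule admits patients who give no follow-up or no exposure. Sections 16.2 and 16.3 assume a different enrolment stop, and the documents do not say which governs.

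Under an assumed 10-30% loss per arm, a stop at 70 gives about 42-73% power (about 50-68% for an even mix). Running to 100 gives about 75-85% if the losses are all cancellations and about 55-80% if they are all never-starters followed at the placebo hazard. About 4 points of any fall from 80% at 70 patients come from the 12-week cap alone (80% to 76%) and should not be charged to drop-out.

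**What to change.** - In 16.11, delete the no-drop-out assumption. Keep all eligible randomised patients in the log-rank test.
- State one accrual stop, identically in 16.11, 16.2 and 16.3: continue, within the existing maximum of 100, until 35 per arm have started product and have a baseline and at least one post-baseline PQL. Cancellations and never-starters then draw on the reserve as 16.2 intends.
- Give one accrual duration to match, and say what happens if 66 events have not occurred when the last patient completes 12 weeks.
- Replace the 80% with power for this analysis as a range over stated assumed loss rates, and give the no-loss reference with the 12-week cap (about 76% at 35 per arm) separately. At 30% loss the stop falls at 35/0.70 = 50 per arm, with power of about 55-75% depending on the type of loss.

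The cost is a change of wording, a less favourable printed power, and possibly a longer accrual than a stop at 70. No patient is added beyond the stated maximum. Starters must be counted by arm, so the count should be kept by staff who hold the codes.

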3.2 Exclusion Criteria

- 3.21 Symptomatic and/or untreated brain metastases.
- 3.22 Ongoing parenteral nutrition (receiving intravenous nutrition support at the time of enrollment). Note: patients may be receiving maintenance IV fluids.
- 3.23 Current enrollment in any other trial that entails the concurrent administration of any other agent designed to enhance postoperative recovery.
- 3.24 Allergy to beef.

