10.3 Assessment of Attribution

When assessing whether an adverse event is related to a medical treatment or procedure, the following attribution categories are utilized:

Definite - The adverse event is *clearly related* to the agent(s).
Probable - The adverse event is *likely related* to the agent(s).
Possible - The adverse event *may be related* to the agent(s).
Unlikely - The adverse event is *doubtfully related* to the agent(s).
Unrelated - The adverse event is *clearly NOT related* to the agent(s).

Events determined to be possibly, probably or definitely attributed to a medical intervention suggest there is evidence to indicate a causal relationship between the agent and the adverse event.

10.4 Expedited Reporting Requirements for Commercial Agent(s) ONLY:

Expedited Reporting Requirements for Adverse Events that Occur in a Non-IND/IDE trial within 30 Days of the Last Administration of a Commercial Agent^{1,2}

ALL SERIOUS adverse events that meet the above criteria **MUST** be immediately reported to the sponsor within the timeframes detailed in the table below.

Hospitalization	Grade 1 Timeframes	Grade 2 Timeframes	Grade 3 Timeframes	Grade 4 & 5 Timeframes
Resulting in Hospitalization ≥ 24 hrs		7 Calendar Days		24-Hour 3 Calendar Days
Not resulting in Hospitalization ≥ 24 hrs	Not required		7 Calendar Days	

NOTE: Protocol specific exceptions to expedited reporting of serious adverse events are found in section 10.41 of the protocol.

Expedited AE reporting timelines are defined as:

- “24-Hour; 3 Calendar Days” - The AE must initially be reported via MedWatch within 24 hours of learning of the AE, followed by a complete expedited report within 3 calendar days of the initial 24-hour report.
- “7 Calendar Days” - A complete expedited report on the AE must be submitted within 7 calendar days of learning of the AE.

¹Serious adverse events that occur more than 30 days after the last administration of investigational agent/intervention and have an attribution of possible, probable, or definite require reporting as follows:

Expedited 24-hour notification followed by complete report within 3 calendar days for:

- All Grade 4, and Grade 5 AEs

Expedited 7 calendar day reports for:

- Grade 2 adverse events resulting in hospitalization or prolongation of hospitalization
- Grade 3 adverse events

Effective Date: May 5, 2011

Additional Instructions:

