We expect about 10% of patients to experience grade 3 or worse adverse events (at least possibly related to the study intervention). In addition, we expect less than 1% of patients to experience a Grade 5 adverse event, at least possibly related to the study intervention. Accrual will be temporarily suspended to this study if at any time we observe adverse events that satisfy any of the following within each arm separately (i.e. if any of the following occur in arm A or arm B, we will suspend accrual to the trial):

- If at any time 4 or more in the first 20 treated patients (or 20% or more after the first 20) experience a Grade 3 or worse adverse event (possibly, probably, or definitely related to the intervention).
- If at any time, 1 patient experiences a grade 5 adverse event (possibly, probably, or definitely related to the intervention).

We note that we will review all Grade 5 adverse events on a case-by-case basis as well (regardless of attribution), and may suspend accrual after just one Grade 5 event, if we feel it is necessary for patient safety.

16.6 Definitions and Analyses of Secondary Endpoints: All these endpoints will be assessed individually and will also be compared between the 2 arms. Monthly phone calls may be used to collect the secondary endpoint information for each patient, including adverse events, surgical complications, and other data (e.g. patient reported weight, intervention compliance, etc.). We will be assessing, reporting on, and potentially analyzing all the data collected from these monthly telephone calls.

16.61 Adverse Events: All eligible patients who have initiated therapy will be considered evaluable for adverse event analyses. The maximum grade for each type of adverse event will be recorded for each patient up to 16 weeks post-randomization (12 weeks of intervention + 1 month post-intervention observation timepoint), and frequency tables will be reviewed to determine adverse event

patterns. The overall adverse event rates for grade 2 or higher adverse events, will be compared using Chi-Square or Fisher's Exact tests. In addition, the surgical complication rates (up to 1 month post-surgery) will also be compared between the 2 arms using Chi-Square or Fisher's Exact tests.

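### The adverse event analysis leaves out patients who took study product but were later found ineligible, although the stopping rule counts all treated patients

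*Combined protocol and SAP*

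**What the plan says.** Section 16.61 gives the only analysis set for adverse events: "All eligible patients who have initiated therapy will be considered evaluable for adverse event analyses". For that set it records the maximum grade of each event type up to 16 weeks after randomization. It compares grade 2 or higher rates between arms by chi-square or Fisher's exact test, which serves goals 2.23 and 2.24.

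Section 13.4 says how eligibility can be lost after entry: "A participant is deemed *ineligible* if after registration, it is determined that at the time of registration, the participant did not satisfy each and every" criterion for entry. The consequence is "The patient will go directly off study". If the participant took study product, "all data up until the point of confirmation of ineligibility must be submitted", and nothing is asked for after that.

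Other sections use exposure rather than eligibility as the base. The stopping rule in 16.52 acts on "4 or more in the first 20 treated patients" in either arm (or 20% or more thereafter) with a related grade 3 or worse event. The expedited reporting table in 10.4 covers events "within 30 Days of the Last Administration of a Commercial Agent", and 10.52 requires reporting of any death within 30 days of the last dose. None of these is limited to eligible patients.

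**The concern.** A safety analysis should describe what happened to everyone exposed to the product. Eligibility under 13.4 is decided after registration and possibly after treatment has begun, so making it a condition for entering the adverse event tables lets a later finding remove exposed patients and events already recorded. The interim safety rule and the final safety tables then rest on different populations.

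There is also one route by which the removal could depend on arm. "Allergy to beef" is an exclusion (3.24), and SBI is a bovine protein. The placebo ingredients listed in 15.12 are dextrose, orange flavor and a coloring, with no bovine protein. If a patient had a beef allergy at registration that nobody knew of, a reaction to SBI might be what brings it to light. She would then be ruled ineligible, and the reaction would drop out of the analysis meant to describe it. At stake is a rare product-related reaction disappearing from the adverse event profile of a pilot meant to inform a larger trial. Section 15.191 itself says that not all side effects are yet known.

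**Working it through.** The point rests on definitions, and there is no figure in the plan to reproduce. The sections are compared first, followed by an illustration of size.

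**Path of a treated patient later found ineligible**

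1. Stopping rule (16.52): she is a treated patient, so a related grade 3 or worse event counts.
2. Follow-up (13.4): she leaves the study, and data are due only up to confirmation.
3. Expedited reporting (10.4, 10.52): serious events and deaths are still reportable for 30 days after the last dose, and later if attributed to the product.
4. Routine reporting (10.6, 10.61): after confirmation, nothing in 13.4 keeps routine collection of non-expedited events going.
5. Final analysis (16.61): she is not eligible, so neither she nor her events enter the profile or the comparison. No other section defines an all-treated set.

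Steps 1 and 5 conflict for the same event. Section 8.0 also sends a patient with a related event of grade 1 or worse to the 4-week observation, and 13.2 sends patients who stop for unacceptable adverse events to the observation phase. Section 13.4 takes her off study if she is also ruled ineligible. The plan does not say which section governs.

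**Size, by illustration**

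The documents do not give the number of treated patients later ruled ineligible. Section 16.2 allows 15 extra per arm, but this pools ineligibility, cancellation, major violation and other reasons, and 13.6 largely defines cancellation as removal before any intervention. It does not estimate this group. The following are assumptions: 50 treated per arm (the accrual maximum in 16.2), and k treated SBI patients later ruled ineligible, all with an event.

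- One of 5 events lost: 5/50 = 10.0% becomes (5 − 1)/(50 − 1) = 4/49 = 8.2%.
- An event seen only in the k patients: the all-treated rate is k/50, that is 2.0%, 4.0%, 6.0% and 10.0% for k = 1, 2, 3 and 5. Under 16.61 it is 0/(50 − k) = 0% each time.
- With 5/50 in each arm also having a grade 2 or worse event for other reasons, the SBI rate is (5 + k)/50 for all treated and 5/(50 − k) under 16.61:

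| k | All treated | Under 16.61 | Fisher p, all treated | Fisher p, under 16.61 |
|---|---|---|---|---|
| 1 | 6/50 = 12.0% | 5/49 = 10.2% | 1.00 | 1.00 |
| 2 | 7/50 = 14.0% | 5/48 = 10.4% | 0.76 | 1.00 |
| 3 | 8/50 = 16.0% | 5/47 = 10.6% | 0.55 | 1.00 |
| 5 | 10/50 = 20.0% | 5/45 = 11.1% | 0.26 | 1.00 |

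No case reaches significance even with every treated patient included. What changes is the description of SBI: an event confined to these patients is reported as never having occurred.

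The relative effect on the overall grade 2 or worse rate shrinks as the background rate rises. At an assumed 22%, 11/50 becomes 10/49 = 20.4%, a relative fall of 7%. At an assumed 50%, 25/50 becomes 24/49 = 49.0%, a relative fall of 2%.

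**The case against.** The strongest reply is that the plan already has a route for a patient who reacts, and it does not lead off study. Sections 8.0 and 13.2 move her to observation, and 15.16 treats a newly developed hypersensitivity as a reason to stop the product, separately from a known allergy. By default she remains eligible and is counted. Ineligibility needs the further finding that a criterion was unmet at registration, and a reaction to a packet that also contains flavoring and coloring does not by itself prove a prior beef allergy. This stands, and it makes the arm-related route narrow.

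A reader might infer that the loss falls only on the SBI arm. The documents do not support that. Laboratory limits, pregnancy test, type and timing of surgery, oral intake and parenteral nutrition are settled at or before registration. Under blinded assignment, ineligibility on those grounds has no evident reason to differ by arm. Only beef allergy offers a plausible asymmetric path.

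A reader might also apply the roughly 10% related grade 3 or worse rate in 16.52 to 35 to 50 patients (3.5 to 5 events per arm), suppose one or two lost, and conclude that 20% to 50% of the SBI rate would vanish. That rate is not the one compared in 16.61, which covers grade 2 or higher events overall, and nothing in the documents supports the one or two.

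Oversight during the trial is also largely intact. The revealing event is submitted, expedited and death reporting continues, and the study team and DSMB review safety (16.51). These safeguards do not place the event in the final tables or keep up routine collection after confirmation. It is fair to add that the 16-week window in 16.61 is, strictly, not promised to a patient outside its analysis set.

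**Conclusion.** The point holds as a gap in the definition of the safety set. Sections 16.61 and 13.4 together drop exposed patients and their events from the adverse event profile and the grade 2 or worse comparison, while 16.52 counts treated patients. The loss is confined to the planned analysis and to non-expedited events after confirmation of ineligibility.

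The number affected is unknown and probably small. On the assumed 50 treated per arm, one lost event of 5 moves 10.0% to 8.2%, and an event seen only in 1 to 5 such patients goes from between 2.0% and 10.0% to zero. The damage is to the adverse event profile, with no illustrated test result crossing significance. Systematic removal of SBI reactors should not be inferred, because it would require a pre-existing, unrecognised beef allergy in each case. This is a cheap improvement to the plan, and the primary comparison is untouched.

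**What to change.** - **16.61:** define the safety set as all patients who took at least one dose of study product, regardless of eligibility. This matches the treated-patient base of 16.52.
- **13.4:** state that going off study for ineligibility does not end adverse event collection for a patient who took any product. Collection should continue at least for the 30 days after the last dose used in 10.4 and 10.52, and preferably to the 16-week point in 16.61.
- **13.4 with 8.0 and 13.2:** reconcile these sections, so that it is clear which governs follow-up when a patient has a related event and is also found ineligible.

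The cost is about one sentence in each of 16.61 and 13.4, a few extra adverse event forms, and a safety denominator slightly larger than under the present rule and no longer confined to the eligible patients used for the primary endpoint. The sample size and the efficacy analysis do not change.
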